1.3 Concurrent Treatment

On the one hand, during the trial, drugs that affect the evaluation of therapeutic efficacy, such as chemotherapeutic drugs, targeted drugs, bio-immune agents, Chinese medicine injections, and other drugs that are clearly indicated in the instructions to be used for anti-tumour purposes, shall not be used in combination. On the other hand, detailed records should be made of the combined diseases or symptoms that existed before the start of the trial, and the drugs or other therapies that need to be continued or added must be recorded in the case report form with the generic name of the drug or the name of the other therapies, the dosage, the reason for use, the number of times of use, and the time of use, etc., so that they can be analysed and reported at the time of the summary.

1.4 Sample Size

The calculation of the sample size of this clinical trial is based on the statistical results of the "Chinese Medicine Clinical Research on Common Malignant Tumours (Lung Cancer)" conducted by this group in the Third Round of Shanghai Three-Year Action Plan of Traditional Chinese Medicine. Based on the group's previous clinical research on the survival and immune function effects on patients after radical NSCLC surgery, the 5-year disease-free survival rate was 90.2% in the treatment group and 78.3% in the control group. Sample size was calculated using PASS.15 software, and Survival-Two Survival Curves-Test(Equality)-Logrank Tests were applied. set Power=0.8, α = 0.025 (unilateral), according to the control group and experimental group 1:1, combined with the basis of the previous research, taking the Proportion Surviving as Input Type, S1(Proportion Surviving - Control) = 0.783, S2(Proportion Surviving - Treatment) = 0.90, T0 (Survival Time) = 5 years, Accrual Time (Integers Only) = 2 years, uniform enrolment, the rate of shedding in each group is 10%, the calculation can be calculated to obtain a total sample size of 317 cases, 158 cases in the treatment group and 159 cases in the control group. At the same time, there are five clinical trial centres in this study, according to the sample size estimation requirements of multifactorial analysis, the introduction of one more confounding factor needs to increase the sample size of each group by 15-25 cases, and this study considers an increase of 20 cases in each group. Therefore, 178 cases need to be collected in each group, and the total sample size of the two groups is 356 cases (Table 2).

Table 2. Sample size estimation for each centre.

research centre	treatment group	control group	total
Shanghai Municipal Hospital of Traditional Chinese Medicine	38	38	76
Shanghai Pulmonary Hospital	35	35	70
Shanghai Chest Hospital	35	35	70
Shanghai General Hospital	35	35	70
Shanghai TCM-Integrated Hospital	35	35	70
total	178	178	356

1.5 Subject Withdrawal

Trial suspension refers to the stopping of a clinical trial in the middle of a trial that has not yet been completed as planned. The purpose of trial suspension is mainly to protect the rights and interests of the subjects, ensure the quality of the trial and avoid unnecessary economic losses. Discontinuation of the trial is required in the following cases: 1. Serious safety problems occurred in the trial, the trial should be promptly suspended; 2. The trial found that the drug treatment effect is too poor, or even ineffective, does not have clinical value, the trial should be discontinued, on the one hand, to avoid delaying the effective treatment of subjects, while avoiding unnecessary economic losses; if there is a disease progression or serious adverse reactions can be initiated by the withdrawal of the protection mechanism, i.e., the inclusion of evaluable cases, the later assessment of efficacy data to invalid for carry-over. The lack or loss of efficacy is assessed by the investigator (not the subject). 3. Significant errors in the clinical trial protocol are identified during the trial, making it difficult to evaluate drug effects; or a well-designed protocol has undergone important deviations in its implementation, and further continuation makes it difficult to evaluate drug effects; 4. The sponsor requests suspension (e.g., financial reasons, management reasons, etc.); 5. Withdrawal of the trial by the administrative authority, etc.

1.6 Compliance

We will record the number of medications returned by participants to calculate utilisation rates. We will take measures to improve adherence, including asking them to complete a statement as part of the informed consent process, emphasising the importance of completing the study.

2 Trial Procedures

2.1 Stratified randomisation and blind implementation

The stratified random grouping scheme used in this study was prepared by a statistician. The entire study population that met the inclusion criteria was allocated according to the stratified random grouping scheme. The sample size for each stratum was a multiple of the group size. The stratification factors were different sub-centres. A teacher of medical statistics, who was not related to the data management and statistical analysis of this trial, generated a random table through Statistical Product and Service Solutions (SPSS) software, and the test group: control group was randomly coded in a ratio of 1:1 using the block randomisation method, and the length of the selected block (block) and the random seed parameter, etc., were sealed together as confidential data in a blinded bottom. After blinding, the blenders of the statistical unit handed over the sealed blenders to the unit in charge of the clinical study, including the first-level blenders and

second-level blinds made according to the random number, and the blinds were sealed in duplicate at the unit in charge of the clinical study.

A two-level blinded design was used, with the first level being the group corresponding to each case number (e.g., group A or group B) and the second level being the treatment corresponding to each group (test or control). The randomised coding table was created by the statistical unit, and the two levels of blinded bottoms were individually sealed in duplicate and stored in the team leader's unit and in the quality control office, respectively. When all the case report forms (CRFs) were entered into the database, and after questioning, verification, and blinding audit, the data were locked (Locked), and the first unveiling of blinding (i.e., clarifying Groups A and B) was carried out by the staff member who kept the blinded bottoms, which was handed over to biostatisticians to enter into the computer, and then statistically analysed after linking up with the data files. When the statistical analyses were completed a second blinding was carried out to clarify the test and control groups.

Blinding may be broken in emergency situations when the investigator believes that knowledge of the medication taken by the subject is beneficial for the management of adverse events. This should be done by the investigator and a detailed record of the reason, time and place of blind breaking should be recorded and signed. Within 24 hours of the blinding, the responsible (lead) unit of the clinical trial and the clinical supervisor as well as the statistically relevant personnel should be notified and the reason for the blinding should be explained. Once the contingency letter has been opened, the numbered subject will be withdrawn from the trial and treated as a dropout case, and the investigator should record the reason for withdrawal on the case report form. All contingency letters will be retrieved at the end of the trial along with the case report form for blinded audit at the end of the trial.

2.2 Method of administration

Chemotherapy regimen selection: chemotherapy regimens will be selected according to NCCN guidelines, and patients will be treated with platinum-based chemotherapy according to one of the following regimens for 3 weeks each for 4 cycles: (1) NP regimen: vincristine, 25mg/m² on day 1, cisplatin, 75mg/m² on day 1; (2) GP regimen: gemcitabine, 1,250mg/m² on days 1 and 8, and 75mg/m² on day 1; (3) DP regimen: docetaxel, 75 mg/m² on day 1 and cisplatin, 75 mg/m² on day 1; (4) AP regimen: pemetrexed, 500 mg/m² and cisplatin, 75 mg/m² on day 1; and (5) TC regimen: paclitaxel, 200 mg/m² on day 1 and carboplatin, area under the curve (AUC) 6 on day 1, and patients intolerant of cisplatin will be given area under the curve (AUC) 5-6 on day 1 (AUC) 5-6 given carboplatin. All chemotherapeutic agents will be administered intravenously in both groups. The chemotherapeutic agents were administered strictly according to the appropriate instructions and NCCN guidelines for recommended dosage, duration and usage.

For oral administration of traditional Chinese medicine, each bag was soaked in 400 ml of boiling water at 100°C for 20 minutes, divided into 2 portions, each with a content of 200 ml. 200 ml was taken orally twice a day, in the morning and in the evening.

2.3 Test period

Chinese medicine treatment period is 6 months. Follow-up period: 3 years after the end of dosing. After the end of the programme, follow-up will continue until 5 years or until the subject dies (or progresses).

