Methods: A multi-centre, double-blind, randomised, placebo-controlled parallel group controlled trial will be conducted. Eligible patients will be randomised into a treatment group (daily Fuzheng Quxie Formula granules + regular chemotherapy) and a control group (daily Chinese medicine placebo granules + regular chemotherapy) in a ratio of 1:1. It is recommended that the participants' chemotherapy be used strictly in accordance with the dosage, duration and usage as recommended in the respective instructions and National Comprehensive Cancer Network (NCCN) guidelines. Fuzheng Quxie Formula was administered orally, twice a day, in the morning and evening, for 6 months. Follow-up after the end of medication, follow-up period of 3 years. After the end of the programme, follow-up was continued until 5 years or until the subject died (or progressed). The primary outcome was disease-free survival (DFS), and the secondary outcomes were overall survival (OS), minimal residual disease (MRD), circulating tumour cells detection, TCM symptom score, assessment of quality of life (QoL), immune indices, tumour markers, peripheral blood systemic immune- inflammation index (SII), prognostic nutritional index (PIN) and prognostic nutritional index (PNI).

Discussion: This will be the first trial to evaluate the efficacy and safety of Fuzheng Quxie Formula in inhibiting metastasis after surgery in stage IIA-IIIA lung cancer with negative driver genes. The results of this randomised controlled trial will fill a gap in this study by showing whether Fuzheng Quxie Formula combined with postoperative chemotherapy improves the prognosis for patients with lung cancer.

Ethics and Dissemination: The Ethics Committee of Shanghai Municipal Hospital of Traditional Chinese Medicine, Shanghai University of Traditional Chinese Medicine approved the study protocol (approval no.: 2023SHL-KY-19-01, 2023/02/23). The study will also be supervised and

managed by the Ethics Committee.

Keywords : Fuzheng Quxie Formula, Lung cancer in stage IIA-IIIA, Negative driver genes, Metastasis after surgery

Background

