2.4 Discontinuation Criteria

First, during the course of medication, if the subject develops an aggravation of the condition

he/she should discontinue the use of the test drug, complete the post-evaluation of the efficacy and the relevant laboratory tests to end the trial, and the subject will be counted as an invalid eligible case for inclusion in the PPS. Second, if the investigator believes that other circumstances make it inappropriate for the subject to continue using the test drug.

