2.5 Data Collection and Management

2.5.1 Data management system

All the original data in the case report form will be backed up and entered into the database by two people, proofread each other and correct the entry errors, and after checking the accuracy with the original data in the case report form, the data will be locked and then statistically analysed. Construct a high-quality clinical research database, incorporate it into the unified management of the big data platform of the Oncology Research Centre, and conduct long-term tracking and follow-up of the research subjects.

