2.6.4 Efficacy indicators

Main efficacy indicator is DFS. Refers to the time between the start of randomisation and disease recurrence or death (from any cause). Imaging: Chest CT examination before the start of treatment and every 6 months after surgery. Patients found to have recurrent metastases were discharged from the group for standardised treatment when the pathological diagnosis was clear. Observation and follow-up until 5 years after surgery, disease-free survival rate, disease-free survival and median survival calculation. Secondary efficacy indexes includes OS, MRD, Circulating tumour cells detection, TCM symptom score, QoL, Immune indicators, Tumour markers, SII, PIN, PNI.

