OS: Endpoint indicator, defined as the time from the start of randomisation to death due to any cause. Overall survival and median survival calculations were performed with observational follow-up up to 5 years postoperatively. MRD: Second-generation sequencing NGS method is used to detect MRD in peripheral blood of the study subjects to obtain the superior population screening model for TCM treatment; Circulating tumour cell detection: Detect 1 time each before and after intervention. Specimen collection method: 10ml of venous blood was taken from the patient's median elbow vein with EDTA blood collection tube, the blood collection tube was repeatedly inverted and mixed, centrifuged at 2000g for 10min, the supernatant was retained, and in order to further remove the redundant cellular components, it should be centrifuged again at 8000g for 10min. Separated plasma was frozen and stored at -80°C or extracted immediately according to the extraction kit instruction steps respectively. The remaining blood cells should be added to saline to replenish 10ml and then immediately isolate the circulating tumour cells. TCM symptom score: According to the "Shanghai TCM disease diagnosis and treatment routine", 10 TCM symptoms of cough, sputum, chest pain, chest tightness, shortness of breath, fatigue, loss of appetite, insomnia, dry mouth and throat and spontaneous sweating were observed, and the severity was scored according to 0-3, which was recorded once before and 6 months after the intervention. Significant effect: the reduction of TCM symptom score is greater than or equal to 70% after the intervention; Effective: the reduction of TCM symptom score is greater than or equal to 30% and less than 70% after the intervention; Ineffective: the reduction of TCM symptom score is less than 30% after the intervention or elevated compared with the previous one. Quality of life assessment: The Quality of Survival Scale for Lung Cancer Patients EORTC QLQ-LC43 was used, which consists of EORTC QLQ-C30 (core scale) and EORTC QLQ-LC13 Th (characteristic subscale of lung cancer). It mainly scores lung cancer patients on 5 domains related to functioning, general clinical symptoms, characteristic sub-symptoms, general health status and

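### Overall survival is to be followed to 5 years, but the follow-up rules stop at progression and discharge relapsed patients, so deaths after relapse may never be collected

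*Protocol*

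**What the plan says.** The OS definition in Protocol 2.6.4 is clear: "OS: Endpoint indicator, defined as the time from the start of randomisation to death due to any cause". Its horizon follows: "Overall survival and median survival calculations were performed with observational follow-up up to 5 years postoperatively".

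Three other rules bear on how long a relapsed patient is observed:

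- Section 2.3 sets 6 months of dosing and 3 years of follow-up, and then: "After the end of the programme, follow-up will continue until 5 years or until the subject dies (or progresses". The Methods part of the abstract carries the same rule: "After the end of the programme, follow-up was continued until 5 years or until the subject died (or progressed".
- Section 2.6.4, under DFS: "Patients found to have recurrent metastases were discharged from the group for standardised treatment when the pathological diagnosis was clear".
- Section 2.4 says that a subject whose condition worsens during medication stops the test drug and is to "complete the post-evaluation of the efficacy and the relevant laboratory tests to end the trial".

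The nearest text to a promise of continued observation is in 2.5.1, where the database plan is to "conduct long-term tracking and follow-up of the research subjects". It mentions neither relapse nor vital status.

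**The concern.** Stopping at progression suits DFS, where relapse is itself the event. It does not suit OS, because most deaths in resected lung cancer can be expected to come after a relapse. The protocol never separates three different things: the end of study treatment, the DFS event and the end of survival follow-up.

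If a site ends observation at relapse, OS is censored there. That censoring is informative, because a patient who has just relapsed has a much higher risk of death than one who has not. The Kaplan-Meier curve and the Cox hazard ratio planned for OS would then mainly describe death without recurrence. If the stop is applied less widely, fewer deaths are lost, but the loss still falls only on patients who progressed. Five centres may read the wording in different ways, so the loss could also differ by centre.

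**Working it through.** **Wording, side by side.** The OS text sets a 5-year horizon for death from any cause. The text in 2.3 and the abstract ends the extended phase, which starts about 6 months + 3 years = 3.5 years after treatment begins, at death or progression. So a patient who progresses at year 4 is past the stop in 2.3 but still inside the OS horizon of 2.6.4. For earlier relapses the discharge rule (2.6.4) and the end-of-trial rule (2.4) apply. Each can be read as ending treatment only or as ending observation.

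The protocol gives no event count or power for OS, so there is no OS figure to reproduce. The size below is an illustration.

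**Inputs from Protocol 1.4:** 5-year DFS of 0.783 (control) and 0.90 (treatment), and 178 patients per group.

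**Assumptions not in the documents:**
- constant hazards;
- a share f of first DFS events that are deaths without relapse, 5-20% (central 10%);
- exponential survival after relapse with median 1-3 years (central 2);
- a 5-year clock from randomisation, with dosing ending at 0.5 years and the programme at 3.5 years.

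**Hazards, control arm, central case.**
- First event: h = -ln(0.783)/5 = 0.0489 per year.
- Relapse: r = 0.90 × h = 0.0440.
- Death without relapse: d = 0.10 × h = 0.0049.
- Death after relapse: m = ln 2 / 2 = 0.3466.

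**True 5-year deaths.**
- Without relapse: f × (1 - 0.783) = 0.0217.
- After relapse: ∫₀⁵ r e^(-hu) [1 - e^(-m(5-u))] du = 0.1056.
- Total 0.1273, so true OS is 0.873. Among 178 patients this is 3.9 + 18.8 = 22.7 deaths.

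**Deaths unobserved, by reading of the rules.**

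| Reading | Probability of an unobserved death (central) | Share of deaths (central) | Range over assumptions |
|---|---|---|---|
| (a) Stop applies only to progression after 3.5 years; discharge means off study treatment. Integral above taken from 3.5 to 5 | 0.0119 | 9.4% | 6-13% |
| (b) As (a), and relapse during dosing ends the trial. Add the integral from 0 to 0.5 | 0.0119 + 0.0176 = 0.0295 | 23.2% | 17-27% |
| (c) As (a), and earlier relapsers alive at 3.5 years are not followed further. Add ∫₀^3.5 r e^(-hu) [e^(-m(3.5-u)) - e^(-m(5-u))] du | 0.0119 + 0.0327 = 0.0446 | 35.1% | 28-40% |
| (d) Observation ends at relapse | 0.1056 | 83.0% | 63-93% |

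With 5-year DFS varied from 54.5% to 90%, the ranges become 5.5-14%, 17-27%, 26-40% and 62-94%. The 54.5% comes from the 45.5% recurrence quoted in the Background for stage II-III, with a 5-year horizon assumed. The shares hardly depend on the planning rate.

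**Effect on the OS estimate under (d), central case.** Apparent control OS is e^(-5d) = 0.783^0.10 = 0.976, against a true 0.873. The between-arm result depends on whether the formula also affects death without relapse. Taking that hazard ratio from 1.0 down to ln 0.90 / ln 0.783 = 0.43:
- deaths in both arms: 33-34, of which 6-8 are seen;
- true OS difference: 6.3-6.9 percentage points;
- apparent OS difference: 0-1.4 points.

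**The case against.** The strongest reply is that the OS text is specific and unqualified, and a specific endpoint rule normally governs a general parenthesis. On that view the mention of progression in 2.3 merely names the DFS event beside the OS event. Discharge for standardised treatment means leaving the allocated regimen, and the sentence after it in 2.6.4 again speaks of observation to 5 years. Section 2.4 concerns stopping the test drug, and its trigger, a worsening of the condition, is not equated with relapse. The Statistical Analysis section also calls for intention-to-treat.

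Much of this is fair. The stop in 2.3 literally covers only the phase after about 3.5 years, and reading (d) is a worst case, not a stated rule. Reading (b) needs two inferences: that early relapse triggers 2.4, and that ending the trial ends follow-up for death. The absolute figures are illustrative: a true control OS of 0.873 lies above the 5-year survival that the Background quotes for stages IIA, IIB and IIIA (78.2%, 62.9% and 49.3%). OS is secondary and carries no power claim.

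It does not remove the conflict. The stop at progression is written twice, and no sentence overrides it for survival. An intention-to-treat analysis cannot include deaths that sites were not asked to collect. Even reading (a), the most favourable that still applies the written stop, loses some deaths, all in patients who progressed.

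**Conclusion.** The concern holds, and the text should be fixed. The follow-up rules in 2.3 and the abstract contradict the OS horizon in 2.6.4, and the discharge and discontinuation rules leave earlier relapses open to the same loss. Whether deaths are lost depends on how sites act, so censoring of OS at relapse is a risk and not a certainty. Under the stated assumptions, 6-13% of 5-year deaths are unobserved on the narrow reading and 63-93% if observation ends at relapse. In that worst case the OS comparison is close to uninformative. The shares rest on assumed values for death without relapse and survival after relapse. The contradiction in the wording does not. The primary endpoint DFS is not affected.

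**What to change.** Reconcile the abstract with 2.3, 2.4 and 2.6.4:

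- For survival follow-up, remove the bracketed reference to progression from 2.3 and from the abstract.
- State that relapse, discharge from the group, ending the trial under 2.4 or the end of study treatment does not end follow-up for vital status.
- State that this follow-up continues for every randomised patient to 5 years after surgery, by telephone or records.
- State that OS is censored only at the date last known alive. If an analysis plan already says so, the protocol need only make sure that the date is collected.

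This takes no position on when study treatment stops or how relapse is treated.

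The cost is a few sentences, plus vital-status contacts for relapsed patients. These could follow the 6-monthly rhythm already used for safety tests and chest CT. Those visits are not themselves vital-status contacts, so the contact has to be added explicitly. It should be done while relapsed patients can still be traced.
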